A CT scan will be made at V1 according to the CT Scan Manual and assessed by the central reading site at V2 to provide the current the maximum minor-axis AAA diameter for assessment of eligibility.

It is recommended to complete all of the screening procedures in a one-day Screening Visit (V1), however it is permissible to complete the procedures over multiple days prior to the Baseline Visit (V2), if required.

The Baseline Visit (V2, Day 1):

Some eligibility criteria including smoking status will be re-confirmed. Enrollment into the SC, IQOS and CC arm occurs at V2 after checking that all eligibility criteria are met. Patients who do not meet the eligibility criteria prior to enrollment will be considered as screen failures.

Spot urine and blood samples will be collected, and further assessments will be performed according to the schedule of events (Appendix 1).

Patients who are current CC smokers and not willing to quit smoking after having been advised to quit smoking will be randomized at V2 with a 1:1 ratio within the corresponding stratum (as per stratification criteria) into the following study arms:

- IQOS arm: patients, switching to using IQOS
- CC arm: patients, continuing smoking CC

Using the CT scan made according to the CT Scan Manual at V1 and assessed by the central reading site, patients considered eligible for randomization will be randomized according to the following stratification criteria:

- Aortic maximum minor-axis diameter (male patients: < 40 mm and \geq 40 mm; female patients: < 35 mm and \geq 35 mm)
- Sex (male vs. female)

Confidentiality Statement

Data and information contained in this document are considered to constitute trade secrets and confidential commercial information, and the legal protections provided to such trade secrets and confidential information are hereby claimed under the applicable provisions of applicable law. No part of this document may be publicly disclosed without the written consent of Philip Morris Products S.A.

Patients will be informed of their randomized study arm at V2.

All patients will be advised to use their assigned product until they complete the study.

The Investigational Period: the *ad libitum* exposure period from the check-out from V2 until the end of V8:

The Investigational Period will last up to 3 years following V2 and will include up to 61 months of retrospective (prior to V2) data collection for all enrolled/randomized patients.

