5 STUDY POPULATION

5.1 Selection of Study Population

5.1.1 Inclusion Criteria

Each patient to be enrolled must meet the following criteria:

Study Population and Main Criteria for Inclusion (all study arms):

Female or male Japanese patients with diagnosed AAA meeting the following main inclusion criteria will be enrolled in the study:

1. Patient is aged ≥ 50 years (to be checked at V1).
2. Patient is Japanese (to be checked at V1).
3. Patient diagnosed with AAA (infrarenal, fusiform type) with a current aortic maximum minor-axis diameter of 30 to ≤ 49 mm (in male patient) and 30 to ≤ 44 mm (in female patient).
 - a) Diagnosis of AAA within the past 60 months with at least two computerized tomography (CT) assessments since diagnosis. The two CT scans must have been done within the last 30 months before the Screening Visit (V1) with a time difference of at least 20 weeks and must show an increase of the aortic maximum minor-axis diameter between the first and the latter of these 2 CT scans (to be checked at V1).
 - b) The maximum minor-axis AAA diameter to be used for assessment of eligibility is the maximum minor-axis AAA diameter available at the time of enrollment (based on the CT scan made according to the CT Scan Manual at V1 and assessed by central reading site (to be checked at V2).
4. Patient has smoked commercially available and/or roll-your-own CC on a daily basis for at least 5 years prior to AAA diagnosis, based on self-reporting (to be checked at V1).
5. Patient is ready to comply with the study protocol (e.g., to use their assigned product/regimen during the course of the study) (to be checked at V1 and V2).

Confidentiality Statement

Data and information contained in this document are considered to constitute trade secrets and confidential commercial information, and the legal protections provided to such trade secrets and confidential information are hereby claimed under the applicable provisions of applicable law. No part of this document may be publicly disclosed without the written consent of Philip Morris Products S.A.

Specific to patients screened for enrollment and randomization to the CC or IQOS arms:

Female or male Japanese adult smokers with diagnosed AAA meeting the following additional main inclusion criteria will be enrolled and randomized in the CC and IQOS arm of the study:

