6.4.2 SC Arm

Patients who had stopped smoking will be enrolled in the SC arm at Baseline Visit (V2) through the Interactive Web and Voice Response System (IXRS) without being randomized.

Confidentiality Statement

Data and information contained in this document are considered to constitute trade secrets and confidential commercial information, and the legal protections provided to such trade secrets and confidential information are hereby claimed under the applicable provisions of applicable law. No part of this document may be publicly disclosed without the written consent of Philip Morris Products S.A.

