9.5.2 Secondary Analyses

9.5.2.1.1 Time to Event

Time from Diagnosis of the AAA until Open Surgical AAA Treatment or AAA Endovascular Repair		
Population	:	FAS
Group	:	
• Study Arm• Product Use Category
Contents		
• Create a Kaplan Meier curve for the following events
➢ Open surgical or endovascular repair of AAA➢ Rupture of AAA• Calculate the number of subjects at risk for each of the group.
Definitions		
• Calculate the time to the event by the following equation.
➢ Open surgical or endovascular repair Date of decision to perform surgery – date of diagnosis + 1 = time to the event➢ Rupture of AAA Date of AAA rupture – date of diagnosis + 1 = time to the event• Censor: if a subject does not experience the event, then treat the subject event as censor. Use the last subject visit date.

Confidentiality Statement

Data and information contained in this document are considered to constitute trade secrets and confidential commercial information, and the legal protections provided to such trade secrets and confidential information are hereby claimed under the provisions of applicable law. No part of this document may be publicly disclosed without the written consent of Philip Morris Products S.A.

Time from Diagnosis of the AAA until Open Surgical AAA Treatment or AAA Endovascular Repair	
Remarks	: The date of actual performance of surgery is not determined from the CRF. Instead, the date of decision to perform the surgery will be used for open surgical or endovascular repair of AAA.
Program	Time (months) = (Date of Event – date of diagnosis + 1) / 30.4375 proc lifetest data=BMT plots=survival (atrisk=0 to 18 by 6); time time*status(0); strata group; run; Output Kaplan-Meier estimates at each fixed time point (6, 12, 18, 24, 30, 36 months) along with their 95% CIs. 95% confidence limits are calculated by log-log transformation using standard error (SE) derived by Greenwood's Formula. Also, 25 th percentile, median, and 75 th percentile of Survival time with their respective 95% confidence intervals

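### Kaplan-Meier time from AAA diagnosis counts the event-free months before V2 as time at risk; label it as conditional and add a curve that starts at V2

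*SAP*

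**What the plan says.** SAP 9.5.2.1.1 computes the time for both repair (date of decision) and rupture as the event date minus "date of diagnosis + 1 = time to the event". Patients without the event are censored at their last visit. The PROC LIFETEST code names a time and a status variable but no entry time. The SAP then asks: "Output Kaplan-Meier estimates at each fixed time point (6, 12, 18, 24, 30, 36 months) along with their 95% CIs". The at-risk counts are requested with "plots=survival (atrisk=0 to 18 by 6", so they stop at month 18. Both scales run from diagnosis.

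Observation starts later. Protocol section 4 states: "Enrollment into the SC, IQOS and CC arm occurs at V2 after checking that all eligibility criteria are met". For the cessation arm, Protocol 6.4.2 states: "Patients who had stopped smoking will be enrolled in the SC arm at Baseline Visit (V2". The inclusion criteria require "Diagnosis of AAA within the past 60 months with at least two computerized tomography (CT) assessments since diagnosis", and the two scans must lie before V1 "with a time difference of at least 20 weeks". Protocol section 4 adds that the Investigational Period "will include up to 61 months of retrospective (prior to V2) data collection for all enrolled/randomized patients".

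Eligibility also needs a current aneurysm within the sex-specific diameter limits on the V1 scan (Protocol 5.1.1). Repair and rupture are mandatory reasons for discontinuation (5.2.1). Repair decisions are scheduled for recording at V3 to V8 only (Appendix 1).

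**The concern.** A patient whose aneurysm was repaired or ruptured soon after diagnosis cannot be in the data, yet every enrolled patient counts as at risk from the day of diagnosis. The months between diagnosis and V2 enter the denominator although no event could be observed in them. This is left truncation that the analysis ignores, and neither SAP 9.5.2.1.1 nor SAP section 7 mentions it or says that the estimate is conditional.

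This is the only planned estimate for secondary objective 1. The tabulated times of 6 to 36 months match V3 to V8 on a V2 clock but are applied to the diagnosis clock. A patient diagnosed more than 36 months before V2 is event-free by selection at all six, and none of that patient's follow-up informs any of them. Groups with different lags could also show different curves at the same underlying risk. The groups most exposed to this are the non-randomised SC arm and the product use categories.

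**Working it through.** **Range of the lag L (diagnosis to V2), from the documents.** Maximum: 60 months + 28 days / 30.4375 = 60.9 months, which reproduces the protocol's 61. Minimum under the current criteria: 20 weeks = 140 / 30.4375 = 4.6 months. Protocol 7.4.3, with about 6 months after diagnosis to attempt to stop smoking, points to slightly more.

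**Month 6.** Only a patient with L below 6 months can have an event before month 6, so the estimate there is about 1.00 by design.

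**What the tabulated values are.** Without dropout, follow-up on the diagnosis clock lasts at least 4.6 + 36 = 40.6 months. Even if all six visits come 14 days early (84 / 30.4375 = 2.8 months), it lasts 37.8 months. Nobody is then censored before month 36, and each value is the raw proportion of enrolled patients without an event by that time after diagnosis.

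**Share of time before V2 (no hazard needed).** The documents do not give the distribution of L. Assume it uniform from 4.6 to b months. The share of the first 36 months that precedes V2 is E[min(L, 36)] / 36:

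- b = 18: 11.3 / 36 = 31%
- b = 31: 17.8 / 36 = 49%
- b = 61: 27.3 / 36 = 76%; here (61 - 36) / 56.4 = 44% of patients have a lag over 36 months

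**Constant hazard h per year after V2 (assumed, independent of L).** The SAP value at month 36 is E[exp(-h·max(36 - L, 0)/12)]. The delayed-entry value is exp(-h·31.4/12), where 31.4 = 36 - 4.6. For b = 61 and h = 0.05, the SAP value is [(1 - 0.8774)·12/0.05 + 25] / 56.4 = 0.965.

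| h per year | Delayed entry | SAP, b = 18 / 31 / 61 | Gap, points |
|---|---|---|---|
| 1% | 0.974 | 0.980 / 0.985 / 0.993 | 0.5 / 1.1 / 1.9 |
| 5% | 0.877 | 0.902 / 0.927 / 0.965 | 2.5 / 5.0 / 8.8 |
| 10% | 0.770 | 0.814 / 0.861 / 0.933 | 4.5 / 9.1 / 16.3 |

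**Diameter-selection model (all inputs assumed).** Diameter at diagnosis is uniform on 30-47 mm, growth is 3 mm/year (SD 1.5), entry requires at most 49 mm at V2, and the event is 55 mm. The 55 mm figure is the indicator in Protocol 2.1, used only as a simulation input. At month 36 the true event-free proportion from diagnosis is 0.862. The SAP method gives 0.915 / 0.949 / 0.969 and delayed entry gives 0.915 / 0.946 / 0.949, so the gaps are 0.0 / 0.3 / 2.0 points. At 2 mm/year (SD 1.2) the gaps are at most 0.5 points. Most of the distance to 0.862 is selection on the V1 diameter, which delayed entry does not remove.

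**How often there is no gap.** The gap at month 36 is zero if no event falls within 36 months of diagnosis. With an assumed 11 patients per arm (32 / 3, from the 32 enrolled in Protocol 4.4), the probability is the SAP value to the power 11: 80-92%, 32-68% and 10-47% at 1, 5 and 10% per year.

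**Effect of unequal lags.** At the same 10% per year, lags of 4.6-24 months give 0.836 at month 36 and lags of 36-61 months give 1.000. Curves from V2 agree: simulated 0.742 and 0.741, against exp(-0.3) = 0.741.

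**The case against.** The SAP does what the protocol asks: secondary objective 1 names time from diagnosis. That stands. A V2 curve does not measure time from diagnosis, so it cannot replace the planned display, and adding it must be recorded in SAP section 7.

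The values are not wrong as proportions of enrolled patients, and the study is descriptive with no hypothesis. That also stands, but estimates, quartiles and 95% confidence intervals will be reported by group, and nothing tells the reader that they are conditional.

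A reader might infer that the curve overstates by some 16 points. The documents do not support a figure: they give neither hazard nor lags. The upper end needs a constant hazard that starts at full strength at V2, which fits poorly with entry at or below 49 mm in men and 44 mm in women.

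A reader might also infer that delayed entry gives the true curve, or that lags differ between arms. The first fails under selection on diameter. The second is undocumented, and randomisation balances the lag between IQOS and CIG in expectation.

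Two inputs are soft. That patients are event-free before V2 is an inference, since no criterion names earlier AAA repair or rupture. The 4.6-month minimum comes from the current criteria, while SAP 3.4 shows enrolment beginning under earlier protocol versions.

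The person-year rates in SAP 9.5.2.1.2 already start at randomization. They serve objective 2 and give no time-to-event curve.

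**Conclusion.** The concern holds in a limited form. As a description of time to repair or rupture after diagnosis, the planned estimate is equal to or above a delayed-entry estimate. It is strictly above once an event occurs while another patient in the group has not yet reached V2. The direction follows from the entry rules and the code. The size depends on assumed lags and hazards: about 0.5 to 16 points at month 36 under a constant hazard, 0 to 2 points when entry depends on diameter, and often nothing in arms of about 11. The defect is a missing condition on the estimate and a missing display on the clock on which patients were observed. It is not a departure from the protocol, and it does not touch the primary growth-rate analysis. It should be corrected because the present table would be read too favourably.

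**What to change.** 1. Add a Kaplan-Meier display from V2 to the repair decision, and one to rupture, by arm. Use the randomisation date for IQOS and CIG and the enrolment date for SC. Give estimates and at-risk counts at 6, 12, 18, 24, 30 and 36 months, and use it to describe the arms over the study period.
2. Record this in SAP section 7 as an addition to the protocol analysis.
3. Keep the diagnosis-origin display for objective 1. Label it as conditional on being event-free and within the diameter limits at V2, and extend its at-risk counts from 18 to 36 months.
4. Tabulate the diagnosis-to-V2 lag by arm (median and range).
5. Delayed entry at V2 is optional, as a sensitivity analysis. In simulations with 11 patients at 5-10% per year, its root mean square error at month 36 was 0.131-0.254, against 0.092-0.181 for the SAP method.

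The cost is one more display, a few lines of code and a few sentences, using dates already held. Protocol 9.3 lets each visit move 14 days from the previous one. If the shifts are symmetric, about half of the patients reach V8 before month 36, so the last at-risk count on the V2 clock roughly halves, while month 30 stays well covered. The change does not make the SC arm comparable with the randomised arms. Nor does it repair the product use categories, which SAP 5.7 sets from use at V3 to V8.

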3.2 Secondary Objectives and Endpoints

The secondary objectives of this study are:

1. To describe the time from diagnosis of the AAA until open surgical AAA treatment or AAA endovascular repair or AAA rupture in patients who switch from smoking CIG to using IQOS, as compared to patients who continue smoking CIG and patients who had stopped smoking.

Endpoints (over the entire study period):

- Date of diagnosis
 - Date of decision to perform open surgical AAA treatment or AAA endovascular repair
 - Date of AAA rupture
2. To describe the number of open surgical AAA treatment or AAA endovascular repair and AAA rupture in patients who switch from smoking CIG to using IQOS, as compared to patients who continue to smoke CIG and patients who had stopped smoking.

Endpoints (number per year across all visits):

- Number of patients with open surgical AAA treatment or AAA endovascular repair annually (based on date of decision to perform open surgical AAA treatment or AAA endovascular repair)
 - Number of patients with AAA rupture annually (based on date of AAA rupture)
3. To evaluate the number of AAA growth above 5 mm in 6 months and the number of patients with an overall maximum minor-axis AAA diameter >55mm in male patients and >50mm in female patients, in patients who switch from smoking CIG to using IQOS, as compared to patients who continue smoking CIG and patients who had stopped smoking.

Endpoints (number per year across all visits):

- Number of patients with an increase in maximum minor-axis AAA diameter of more than 5 mm within 6 months
- Number of patients with an overall maximum minor-axis AAA diameter >55mm in male patients and >50mm in female patients

Confidentiality Statement

Data and information contained in this document are considered to constitute trade secrets and confidential commercial information, and the legal protections provided to such trade secrets and confidential information are hereby claimed under the provisions of applicable law. No part of this document may be publicly disclosed without the written consent of Philip Morris Products S.A

4. To monitor the safety profiles associated with IQOS use, CIG smoking and smoking cessation during the study.

Endpoints (over the entire study period):

- Incidence of Adverse events (AEs) / serious adverse events (SAEs)
- Vital signs - change from Baseline (systolic and diastolic blood pressure, pulse rate and respiratory rate)

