4.2.1 Inclusion Criteria

Main Criteria for Inclusion (all study arms):

1. Patient is aged \geq 50 years (to be checked at V1).
2. Patient is Japanese (to be checked at V1).
3. Patient diagnosed with AAA (infrarenal, fusiform type) with a current aortic maximum minor-axis diameter of 30 to \leq 49 mm (in male patient) and 30 to \leq 44 mm (in female patient).
 - a) Diagnosis of AAA within the past 60 months with at least two computerized tomography (CT) assessments since diagnosis. The two CT scans must have been done within the last 30 months before the Screening Visit (V1) with a time difference of at least 20 weeks and must show an increase of the aortic maximum minor-axis diameter between the first and the latter of these 2 CT scans (to be checked at V1).
 - b) The maximum minor-axis AAA diameter to be used for assessment of eligibility is the maximum minor-axis AAA diameter available at the time of enrollment (based on the CT scan made according to the CT Scan Manual at V1 and assessed by central reading site (to be checked at V2)).
4. Patient has smoked commercially available and/or roll-your-own CIG on a daily basis for at least 5 years prior to AAA diagnosis, based on self-reporting (to be checked at V1).
5. Patient is ready to comply with the study protocol (e.g., to use their assigned product/regimen during the course of the study) (to be checked at V1 and V2).

Specific to patients screened for enrollment and randomization to the CIG or IQOS arm:
Female or male Japanese adult smokers with diagnosed AAA meeting the following additional main inclusion criteria will be enrolled and randomized in the CIG and IQOS arms of the study:

6. Patient has smoked on average > 5 commercially available and/or roll-your-own CIG per day (no CIG brand restriction) for the last 12 months, based on self-reporting (to be checked at V1). Intermittent attempts to quit smoking, with or without NRT use during these attempts, not exceeding 2 months or short-term interruption of smoking, with or without NRT use during the short-term interruption, up to 10 days within the last 12 months will be allowed. Smoking status will be verified based on a urinary cotinine test (i.e., cotinine ≥ 200 ng/mL) (to be checked at V1 and V2).
7. Not intending to quit smoking within the next 6 months after having been advised to quit smoking (to be checked at V1 and V2).

Specific to patients screened for enrollment into the SC arm:

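### The Kaplan-Meier table counts from diagnosis but stops at month 36 (at-risk row at month 18), so a substantial share of study follow-up, possibly most, cannot affect it

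*SAP*

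**What the plan says.** SAP 3.2 heads the dates for secondary objective 1 (diagnosis, decision to repair, rupture) with "Endpoints (over the entire study period").

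SAP 9.5.2.1.1 sets the clock at diagnosis: "Time (months) = (Date of Event – date of diagnosis + 1) / 30.4375". Patients without the event are censored at their last visit ("Use the last subject visit date"). The tabulated output is specified as: "Output Kaplan-Meier estimates at each fixed time point (6, 12, 18, 24, 30, 36 months) along with their 95% CIs". Quartiles of survival time with confidence intervals are also requested. The program line reads "proc lifetest data=BMT plots=survival (atrisk=0 to 18 by 6"), so numbers at risk are printed at 0, 6, 12 and 18 months.

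The lag from diagnosis to entry is bounded by SAP 4.2.1: "Diagnosis of AAA within the past 60 months with at least two computerized tomography (CT) assessments since diagnosis", the two scans being "with a time difference of at least 20 weeks". Protocol section 4 adds a screening period of up to 4 weeks and an Investigational Period of up to 3 years after V2. In Protocol Appendix 1, visits V3 to V8 fall at 6, 12, 18, 24, 30 and 36 months after V2.

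**The concern.** The six tabulated times are exactly the V3 to V8 visit months, which are counted from V2, yet the axis they are applied to is counted from diagnosis. The grid fits a different clock from the one the SAP defines.

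A Kaplan-Meier estimate at month t uses only events up to month t. A repair or rupture more than 36 months after diagnosis therefore changes none of the six estimates or their intervals. A patient diagnosed 36 months or more before V2 cannot contribute an event to the table, but counts as at risk at all six times. An arm with several late repairs could be tabulated as fully event-free throughout. The plotted curve would carry no at-risk counts after month 18, so a reader could not judge how firm its later part is.

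**Working it through.** **Inputs**
- Diagnosis to V1: at least 20 weeks (two scans since diagnosis, that far apart) and at most 60 months (SAP 4.2.1).
- V1 to V2: up to 28 days (Protocol 4 and 4.3).
- Follow-up after V2: up to 36 months (Protocol 4 and 4.3).
- Month length: 30.4375 days (SAP 9.5.2.1.1).

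**The plan's own figure.** Protocol section 4 allows up to 61 months of retrospective data before V2. 60 + 28/30.4375 = 60.9, so it reproduces.

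**Range of follow-up on the SAP's axis.** Let D be months from diagnosis to V2. The minimum is 140/30.4375 = 4.6 and the maximum 60.9. A completer's follow-up runs from D to D + 36, so it ends between 4.6 + 36 = 40.6 and 60.9 + 36 = 96.9 months. Every completer passes month 36.

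**Share of a completer's follow-up beyond horizon H** = (D + 36 − H)/36, limited to 0 to 1. For H = 36 this is D/36; for H = 18 it is (D + 18)/36.

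| D (months) | beyond 36 | beyond 18 |
|---|---|---|
| 4.6 | 13% | 63% |
| 12 | 33% | 83% |
| 18 | 50% | 100% |
| 24 | 67% | 100% |
| 30 | 83% | 100% |
| 36 or more | 100% | 100% |

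**Averages over assumed lag distributions** (the documents give none; completers only)
- Uniform on 5 to 61: [(36² − 5²)/72 + (61 − 36)]/56 = (17.65 + 25)/56 = 76%. With bounds 4.6 and 60.9 the result is also 76%; (60.9 − 36)/56.3 = 44% of patients then enter after the last tabulated time, and 96% of follow-up lies beyond month 18. Exits of 5% to 20% per year lower the 76% to 73% to 75%.
- Uniform on 4.6 to 36: 56%.
- Uniform on 4.6 to 24: 14.3/36 = 40%.
- Uniform on 4.6 to 18: 11.3/36 = 31%.
- Break-even: if all lags are 36 months or less, the share is one half when the mean lag is 18 months.

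**Events.** With lags uniform on 4.6 to 60.9 and an assumed constant hazard of 3%, 5% or 10% per year, about 25% to 26% of study events fall by month 36 and about 5% by month 18.

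**Early estimates.** The code has no entry time, so patients count as at risk from diagnosis although they join event-free at V2. Under the same assumptions the SAP method gives 36-month event-free estimates of 97.9%, 96.5% and 93.3%. The assumed hazards acting from diagnosis imply exp(−3 × 0.03) = 91.4%, exp(−3 × 0.05) = 86.1% and exp(−3 × 0.10) = 74.1%. A longer grid leaves this gap in place.

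**The case against.** A reader might infer that most study follow-up is known to lie beyond the table. The documents do not support that for the 36-month table: it depends on the diagnosis-to-V2 lags, and with lags mostly under 18 months the share is a minority. It is certain only for the 18-month at-risk row.

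A reader might also infer that late repairs and ruptures drop out of the analysis. They do not. The curve is not truncated, the quartiles have no 36-month limit, LIFETEST output is listed by arm and by product use category, and SAP 9.5.2.1.2 gives a person-year rate from randomization over all follow-up, with a patient listing. This stands and limits the point to reporting. It does not remove it. The rate says nothing about time since diagnosis, and a 25th percentile exists only if the curve falls to 75%.

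Nor does the table contradict the endpoint definition in SAP 3.2. The study-period phrase there heads three dates and describes an observation window, not a horizon for survival estimates. The SAP also does not rank the fixed-time table as its main result.

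The at-risk row rests on skeletal code. The dataset name is not defined, no statement produces the fixed-time estimates, and the accompanying text asks for numbers at risk without an 18-month limit. The table shells are in a separate document. That weakens the 18-month point, but the 36-month grid is an explicit text instruction.

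Finally, a table run mechanically to month 96 would be nearly empty at the end. Taking the 32 patients that Protocol 4.4 reports as enrolled, lags uniform on 5 to 61 months and no dropout or events, the three arms together would have 32 × 25/56 = 14 at risk at month 72, 32 × 13/56 = 7 at month 84 and 32 × 1/56 = 0.6 at month 96. This stands and shapes the fix.

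**Conclusion.** The mismatch between axis and grid is established from the text without assumptions. Time is counted from diagnosis, the table ends at month 36, and every completer is followed past it. A substantial share of follow-up, possibly most, cannot affect the six tabulated estimates: 13% to 100% by individual lag, and 76% only on the assumption that lags are uniform on 5 to 61 months. At least 63% of each completer's follow-up lies beyond the coded at-risk row.

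The defect is confined to the fixed-time table and the at-risk row of a secondary endpoint in a descriptive study. No data are lost. It is still worth correcting before database lock, because following the SAP exactly yields estimates and intervals that are blind to late repairs and ruptures.

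**What to change.** - For the diagnosis-origin analysis, tabulate estimates and numbers at risk every 12 months as far as follow-up supports, at most to about 96 months. Show the number at risk beside every estimate, and stop or flag rows where it is very small. Set the code's at-risk option to the same grid, replacing "plots=survival (atrisk=0 to 18 by 6").
- Keep the 6 to 36 month grid, with at-risk counts to 36 rather than 18, only for an analysis whose clock starts at V2.
- Correct the early diagnosis-origin estimates separately, by delayed entry at V2 or by using V2 as the time origin. Extending the grid does not do this.

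The grid change costs one line of SAP text, one code option and a longer table. Delayed entry adds the V2 date as an entry time in the program. No new data are needed, and SAP section 1 allows amendments up to database lock.
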